#### Participants:

NHS staff, 18 years and over, who took part in the 'Psychological impact of the Coronavirus (COVID-19) pandemic and experience: An international survey' study (PIoC19 study; IRAS Project ID 282858; REC reference 20/HRA/1934), and provided informed consent to be contacted for future versions of the study ( $n \approx 3500$ ), will be invited to participate in the 'SYD for NHS' trial via email. Once this pool of potential participants is given the opportunity to participate, then the study will be offered to all NHS organisations who may wish to participate in the trial as Participant Identification Centres (PIC). PIC sites will be provided with an open link of the study website to share with their current staff.

Any interested potential participants will be directed to the study website and asked to familiarise themselves with the information provided in the Patient Information Sheet. Those participants who are interested to take part in the study will be asked to complete questions to confirm eligibility, following which they will be asked to consent to undertake a Hospital Anxiety and Depression Scale (HADS) test. Optional consent to be contacted for future ethically approved research in the field of mental health and digital health technologies will be sought. Potential participants who score between 8-14 inclusive will be eligible, as these scores indicate individuals most likely to benefit from interventions of wellbeing like SYD and to be considered safe as higher scores may indicate depression/anxiety levels needing formal psychological evaluation. Participants with HADS scores 15 and over will be advised that they might need to contact their GP for further support. Individuals with low levels of anxiety often do not engage well with wellbeing measures (Singer et al. 2009).

Following confirmation of informed consent, and confirmed eligibility from the screening questionnaire, participants will be randomised 1:1 to one of two groups: Control Group and Intervention Group. People considered clinically extremely vulnerable for COVID-19, are excluded to avoid conflict with government advice. (https://www.gov.uk/government/publications/guidance-on-shielding-and-protecting-extremely-vulnerable-persons-from-covid-19/guidance-on-shielding-and-protecting-extremely-vulnerable-persons-from-covid-19)

Intervention Group: Participants in the Intervention Group will be asked to complete baseline assessments (Month 0) and download / interact with the SYD app (Months 0-3). Participants will complete monthly assessments for a period of 3 months (Months 1-3) to analyse the primary endpoint. A final assessment will be performed at Month 6, to monitor longer term effects of the intervention.

Control Group: Participants in the Control Group will be asked to complete baseline assessments (Month 0) and monthly assessments (Months 1-3) to provide control data in a comparable population. Participants will be advised that they will be invited to download / interact with the SYD app at Month 4 and that study data collection will continue for further 3 months thereafter (Months 4-6).

Title: Pilot	Title: Pilot evaluation of a personalised, prevention mHealth partner, SYD, and its impact on Quality of Life of NHS staff							
Authors	[name], [name], [name], [name], [name]	Ver.	2.0	Date Authorised	13/04/2022	Page 11 of 24		

Participants in both groups will continue to have access to SYD after the end of the trial for their personal use. The last data capture point will be 6 months after the last participant has entered the trial and completed data entry. Data for the purpose of the study will not be collected beyond the 6-month time point unless otherwise mandated by the data and safety monitoring committee for valid reasons.

### 3.6 Trial Schema

### 3.7 Primary Endpoints

Determine the impact of SYD on Quality of Life of NHS Staff over 3 months, as measured through:

- 1. WHO Quality of Life-BREF (WHOQOL-BREF) survey (Global QOL)
- 2. EuroQoL EQ-5D-5L (Health-related QOL)

### 3.8 Secondary endpoints

- 1. Determine the efficacy of SYD in reducing levels of stress, anxiety and depression, as measured through the Perceived Stress Scale (PSS-4) and Hospital Anxiety and Depression Scale (HADS).
- 2. Determine user satisfaction and engagement with SYD
- 3. Persistence of Primary endpoint changes over 6-month time frame

### 3.9 Statistical analysis and sample size calculation

Approximately 3,500 NHS staff, 18 years and over, who took part in the PIoC19 study, and provided consent to be contacted will be invited to join the SYD for NHS trial.

We estimate that ~800 NHS staff will be interested and eligible to participate. As it is currently not known how many participants are likely to interact sufficiently with SYD and provide sufficient trial data, we have assumed that up to 800 participants will have to be randomised to achieve a target of 500 evaluable participants, 250 in each group. Data on all randomised participants will be evaluated and the drop-out rate in the intervention group will be determined.

As this is a pilot study to evaluate the impact of SYD, and not a superiority trial, we have estimated 500 patients being available to have reasonable confidence intervals of any changes in quality of life scales, if available. A previous study of the eBalance app showed significant lifestyle changes within 14 weeks in 85 participants with only 56 participants using the app (Safran Naimark, 2015).

### 4 Study group

The study participation will be offered initially to healthcare professionals who participated in PIoC19 study. NHS staff, 18 years and over, who took part in the PIoC19 study and provided informed consent to be contacted for future versions of the study will be invited to participate in the SYD for NHS trial. Participants will be asked to undertake the Hospital Anxiety and Depression Scale test and score between 8-14 inclusive to confirm that they remain eligible. It is not expected that sites will be required to confirm ongoing capacity and capability.

Once this pool of potential participant is given the opportunity to participate, the study will then be offered to all NHS organisations who may wish to participate as PIC and offer to their staff aged 18 years and above. Participants will be approached via social media and local Trusts' staff communication which will include an open link to the study website.

### 4.1 Inclusion criteria

- 1. NHS staff with an NHS email address which can be used for this study
- 2. Age  $\geq$  18 years

Title: Pilot evaluation of a personalised, prevention mHealth partner, SYD, and its impact on Quality of Life of NHS staff							
Authors	[name], [name], [name], [name], [name]	Ver.	2.0	Date Authorised	13/04/2022	Page 13 of 24	

- 3. Own a personal smartphone device (iOS or Android-based) which can be used for this study
- 4. Sufficient English language ability to familiarise themselves with and engage with SYD and study assessments
- 5. Hospital Anxiety and Depression Scale (HADS) test score between 8 and 14 inclusive, indicating mild to moderate anxiety or depressive symptoms
- 6. Provision of informed consent

### 4.2 Exclusion criteria

- 1. Unwilling or unable to participate
- 2. Any other concurrent psychological interventions
- 3. Concurrent participation in an interventional clinical trial
- 4. People considered clinically extremely vulnerable from COVID-19: https://www.gov.uk/government/publications/guidance-on-shielding-and-protecting-extremely-vulnerable-persons-from-covid-19/guidance-on-shielding-and-protecting-extremely-vulnerable-persons-from-covid-19/guidance-on-shielding-and-protecting-extremely-vulnerable-persons-from-covid-19/guidance-on-shielding-and-protecting-extremely-vulnerable-persons-from-covid-19/guidance-on-shielding-and-protecting-extremely-vulnerable-persons-from-covid-19/guidance-on-shielding-and-protecting-extremely-vulnerable-persons-from-covid-19/guidance-on-shielding-and-protecting-extremely-vulnerable-persons-from-covid-19/guidance-on-shielding-and-protecting-extremely-vulnerable-persons-from-covid-19/guidance-on-shielding-and-protecting-extremely-vulnerable-persons-from-covid-19/guidance-on-shielding-and-protecting-extremely-vulnerable-persons-from-covid-19/guidance-on-shielding-and-protecting-extremely-vulnerable-persons-from-covid-19/guidance-on-shielding-and-protecting-extremely-vulnerable-persons-from-covid-19/guidance-on-shielding-and-protecting-extremely-vulnerable-persons-from-covid-19/guidance-on-shielding-and-protecting-extremely-vulnerable-persons-from-covid-19/guidance-on-shielding-and-protecting-extremely-vulnerable-persons-from-covid-19/guidance-on-shielding-and-protecting-extremely-vulnerable-persons-from-covid-19/guidance-on-shielding-and-protecting-extremely-vulnerable-persons-from-covid-19/guidance-on-shielding-and-protecting-extremely-vulnerable-persons-from-covid-19/guidance-on-shielding-and-protecting-extremely-vulnerable-persons-from-covid-19/guidance-on-shielding-and-protecting-extremely-vulnerable-persons-from-covid-19/guidance-on-shielding-and-protecting-extremely-vulnerable-persons-from-covid-19/guidance-on-shielding-and-protecting-extremely-vulnerable-persons-from-covid-19/guidance-on-shielding-and-protecting-extremely-vulnerable-persons-from-covid-19/guidance-on-shielding-and-protecting-extremely-vulnerable-persons-from-covid-19/guidance-on-s

### 5 Approaching participants to join the study

The study group will be invited to take part in the SYD for NHS study via email sent by the research team at Southern Health NHS Foundation Trust. Where the prior collected data allows, we will invite staff with NHS email addresses. The invitation will include an outline of the proposed trial and the SYD intervention. Potential participants will be directed to a dedicated study website developed on the Qualtrics online website survey platform. The study website will contain a Participant Information Sheet providing a detailed description of the study, including the SYD intervention, study assessments and risks/benefits of taking part. Potential participants will be encouraged to read the Patient Information Sheet carefully before providing informed consent to undertake the screening assessment and joining the study. Contact for the study team will be provided to answer any questions regarding participation. A SYD familiarisation session may also be provided. Any individual who is currently an NHS staff and aged 18 years, whose organisation has agreed to participate will be approached via social media and local Trusts' staff communication which will include an open link to the study website.

### 5.1 Screening and Eligibility Assessment

Participants who decide to take part in the study will be asked to provide informed consent to complete a brief screening and eligibility assessment on the study website to indicate if they meet the eligibility criteria. This will include completion of a Hospital Anxiety and Depression Scale and a score between 8 and 14. This group is deemed to be a group which will most likely engage with and has a potential to benefit from the SYD intervention.

### 5.2 Informed Consent

Eligible participants will be invited to complete the main study informed consent prior to joining the study. The informed consent procedure will take place online in the form of ticking a tick box. Online versions of the Participant Information Sheet and Informed Consent will be presented to the participants detailing the exact nature of the study, what it will involve for the participant, the implications, benefits and or risks associated with participation in this study. It will be clearly stated that participation is voluntary; participants will be free to withdraw from the study at any time for any reason without prejudice to future care and with no obligation to give the reason for withdrawal.

Title: Pilo	Title: Pilot evaluation of a personalised, prevention mHealth partner, SYD, and its impact on Quality of Life of NHS staff								
Authors	[name], [name], [name], [name], [name]	Ver.	2.0	Date Authorised	13/04/2022	Page 14 of 24			

#### 6 Study interventions

#### Baseline and follow-up assessments

Participants who have provided informed consent will be asked to complete the following baseline self-assessments on the study website at the time of joining the study, monthly for the period of 3 months (month 1 - 3) and at month 6 after joining the study:

- 1. WHO Quality of Life-BREF (WHOQOL-BREF) survey, which consists of 26 items related to the individual's quality of life, mostly referring to the preceding 2 weeks (World Health Organization, 1996).
- 2. EQ-5D-5L survey, which consists of 5 items related to the individual's health-related quality of life and VAS scale (Herdman et al., 2011)
- 3. Perceived Stress Scale (PSS-4) questionnaire, which consists 4 items related to the individual's perceived stress in the preceding month (Cohen, 1988).
- 4. Hospital Anxiety and Depression Scale (HADS) questionnaire, which consists of 14 items related to the individual's perception of anxiety and depression in the preceding week (Zigmond et al., 1983).

#### Interaction with the SYD application

Participants in the Control Group (Group B) will be invited to install and interact with the SYD smartphone mHealth app at Month 4. Participants in the Intervention Group (Group A) will be invited to install and interact with the SYD smartphone mHealth app at Baseline.

#### The following information will be collected from within the SYD app:

- 1. Participant characteristics including age, sex, demographics, self-assigned ethnicity and relevant medical conditions (e.g. Cardiovascular disease, Type 2 Diabetes, hypertension, etc.): will be collected when the participant first interacts with the SYD app
- 2. Self-rated measures related to 9 key dimensions of wellbeing (physical health, emotional health, financial health, purpose, social life, brain power, self-esteem, environment, and career)

Study Intervention	Month 0	Month 1	Month 2	Month 3	Month 4	Month 5	Month 6
Informed consent	Х						
SYD intervention – Control Group					Х	Х	Х
SYD intervention – Intervention		Х	Х	Х	Х	Х	Х
Group							
WHOQOL-BREF - Control Group	Х	Х	Х	Х			Х
WHOQOL-BREF - Intervention	Х	Х	Х	Х			Х
Group							
EQ-5D-5L - Control Group	Х	Х	Х	Х			Х
EQ-5D-5L - Intervention Group	Х	Х	Х	Х			Х
HADS - Control Group	Х	Х	Х	Х			Х
HADS - Intervention Group	Х	Х	Х	Х			Х
PSS-4 - Control Group	Х	Х	Х	Х			Х
PSS-4 - Intervention Group	Х	Х	Х	Х			Х

### 7 Study schedule of assessments

Title: Pilot evaluation of a personalised, prevention mHealth partner, SYD, and its impact on Quality of Life of NHS staff							
Authors	[name], [name], [name], [name], [name]	Ver.	2.0	Date Authorised	13/04/2022	Page 15 of 24	

#### 8 Study duration

The recruitment phase of the study is expected to last for up to 12 months.

The total duration of the trial data collection will be from the date of randomisation of the 1st participant to the date on which the last randomised participant reaches 6 months follow-up time point (including two weeks grace to allow timely response).

Therefore, the key dates of the study are:

- Recruitment start date: 1st June 2021
- Recruitment end date: 15th April 2022
- Study data collection end date: 29th October 2022

Participants in the Control Group (Group B) will complete baseline assessments (Month 0), monthly assessments - control data (Months 1-3) and receive intervention (Months 4-6) / complete follow up assessment (Month 6).

Participants in the Intervention Group (Group A) will complete baseline assessments (Month 0), receive intervention / complete monthly assessments in (Months 1-3). A final assessment will be performed after 3 months (Month 6) to assess longer term effects of the intervention.

We aim to undertake the primary analysis after the last participant in the Intervention Group has reached Month 3 data capture point and completed final data entry. Further analysis to assess longer term effects of the intervention will be undertaken after the final study completion.

### 9 Early Discontinuation/Withdrawal of Participants

During the course of the study a participant may choose to withdraw early at any time and without giving a reason. Participants can withdraw from the study but data obtained up until the point of withdrawal will be retained for use in the study analysis. No further data would be collected after withdrawal.

### 10 Statistics and data analysis

### **10.1 Data handling and analysis**

Study data will be collected via the Qualtrics online website built for this study. The Qualtrics survey software has advanced analytics tools built online and analyses will only be descriptive. Data will be analysed by Investigators at the Sponsor organisation (Southern Health NHS Foundation Trust). No data queries will be raised for participants.

Primary endpoint analysis will be undertaken using data collected throughout a period of 3 months of SYD application usage by the study participants. Further analysis of longer-term effects will be undertaken at 6 months after the participant first interacted with the SYD application.

WHOQOL-BREF surveys will be scored according to the general guidelines (World Health Organization, 1996), deriving scores for the 4 main domains (Physical health, Psychological, Social relationships and Environment).

EQ-5D-5L surveys will be scored according to the general guidelines (Herdman et al., 2011), deriving scores for the 5 main domains of the instrument (Mobility, Self-Care, Usual Activities, Pain/Discomfort and Anxiety/Depression), and

Title: Pilot	Title: Pilot evaluation of a personalised, prevention mHealth partner, SYD, and its impact on Quality of Life of NHS staff								
Authors	[name], [name], [name], [name], [name]	Ver.	2.0	Date Authorised	13/04/2022	Page 16 of 24			

SYD (See Yourself Differently) for NHS the 1-dimensional EQ VAS. An EQ-5D index value will be derived from EQ-5D-5L scores using the latest value set for England (Devlin et al., 2018).

PSS-4 scores will be derived according to the general guidelines (Cohen, 1988).

HADS scores will be subdivided into anxiety (HADS-A) and depression (HADS-D) subdomains and scored according to general guidelines (Zigmond et al., 1983).

WHOQOL-BREF, 5Q-5D-5L, EQ-5D index, HADS-A, HADS-D and PSS-4 scores will be modelled using linear mixed effects models. These models will be used to test the effect of group, time of measure and app-related metrics such as type of recommendations done by participants and level of interaction with the SYD app. Baseline characteristics of participants will be used to adjust the models. Imputation procedures will be used to impute missing values where deemed plausible. Effect size measures and p-values will be reported for all group comparisons. The Null hypothesis is of no significant change in Quality of Life.

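### Section 10.1 describes the primary analysis data by SYD usage, which controls cannot have in Months 0-3 and which conflicts with evaluating all randomised participants

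*Protocol*

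**What the plan says.** Two sentences in Protocol Section 10.1 describe which data the analyses use. On the primary endpoint: "Primary endpoint analysis will be undertaken using data collected throughout a period of 3 months of SYD application usage by the study participants". On persistence: "Further analysis of longer-term effects will be undertaken at 6 months after the participant first interacted with the SYD application". Both refer to app use, and neither has separate wording for controls.

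Section 3.9 explains the recruitment target in similar terms: "As it is currently not known how many participants are likely to interact sufficiently with SYD and provide sufficient trial data", it is assumed that "up to 800 participants will have to be randomised to achieve a target of 500 evaluable participants, 250 in each group". No threshold is given for sufficient interaction. The same paragraph then says: "Data on all randomised participants will be evaluated and the drop-out rate in the intervention group will be determined".

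Elsewhere the protocol works in study months. Section 3.5 has both groups assessed at baseline and at Months 1-3, and brings controls onto SYD at Month 4. Section 6 counts the assessments, including Month 6, from joining the study. Section 3.5 also says "Data for the purpose of the study will not be collected beyond the 6-month time point", unless the data and safety monitoring committee requires otherwise. Section 8 sets the timing: "We aim to undertake the primary analysis after the last participant in the Intervention Group has reached Month 3 data capture point".

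**The concern.** The strength of this design is the randomised comparison over Months 0-3, when one group is offered SYD and the other is not. A data rule based on app usage does not fit that comparison. Controls have no usage in the window, and for the intervention group usage is something that happens after randomisation and that participants choose.

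If the usage wording were followed in the intervention group, SYD users would be set against an unselected control group. Any difference in prognosis between people who take up an app and people who do not would then be counted as an effect of SYD. The trial is unblinded, so a choice between two incompatible readings could be made with results in view.

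A related risk lies in the model description in Section 10.1, which lists app-related metrics beside group and time. These are post-randomisation variables with no control counterpart before Month 4. If they entered the model that estimates the group effect, that estimate would no longer be the effect of being offered SYD.

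**Working it through.** **1. Can the wording be applied?** Setting Sections 10.1 and 3.9 against the schedule in Sections 3.5, 6 and 8:

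| Term | Intervention group | Control group |
|---|---|---|
| Three months of SYD usage (10.1) | Matches Months 0-3 only for those who start at about baseline; undefined for those who never open the app | None in Months 0-3; the first usage period is Months 4-6, with one scheduled assessment, at Month 6 |
| Six months after first interaction (10.1) | About Month 6 if started at baseline, later if started later; undefined for never-users | Month 4 + 6 = about Month 10, after collection ends at Month 6 |
| Sufficient interaction (3.9) | Possible, but no threshold | Not possible before Month 4 |
| All randomised evaluated (3.9) | Possible | Possible |

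Only the last row works in both groups over the randomised window.

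**2. The plan's own figure.** Section 3.9 gives 800 randomised for 500 evaluable. The implied non-evaluable share is 1 - 500/800 = 0.375, or 150 of 400 per arm. Checking back, 500/(1 - 0.375) = 800. This is consistent but circular, because the protocol states no loss rate, effect size, SD, alpha or power. (The Section 1 summary gives 500 as the number randomised; the figures here use Section 3.9.)

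If low app use alone caused the loss, it could act only in the intervention arm, leaving 250 + 400 = 650. Reaching 250 in each group needs 150 controls lost for other reasons, such as missing data. So the 37.5% cannot all be read as non-use.

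**3. What following the usage wording could do.** Assumptions, none from the documents:
- SYD has no effect.
- A share q of the 400 intervention participants is dropped for non-use, and all 400 controls are kept.
- Users' prognosis is g SD better than non-users'.
- The test is a two-sided 5% z-test with outcome SD 1 and no baseline adjustment.

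Formulas:
- The full-arm mean is the user mean minus q × g, so dropping non-users gives bias = q × g.
- SE = sqrt(1/400 + 1/(400(1 - q))).
- Rejection rate = 1 - Φ(1.96 - bias/SE) + Φ(-1.96 - bias/SE).

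Example with q = 0.375, g = 0.2: bias = 0.075; SE = sqrt(1/400 + 1/250) = 0.0806; bias/SE = 0.93; rejection rate about 0.153.

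| q (arms) | g = 0.2 | g = 0.3 | g = 0.5 |
|---|---|---|---|
| 0.375 (250 v 400) | bias 0.075, error 15% | 0.113, 29% | 0.188, 64% |
| 0.20 (320 v 400) | 0.040, 8% | 0.060, 13% | 0.100, 27% |
| 0.10 (360 v 400) | 0.020, 6% | 0.030, 7% | 0.050, 11% |

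**4. Precision.** The 95% half-width is 1.96 × sqrt(1/n1 + 1/n2). For 400 v 400 it is 0.139 SD, for 250 v 400 it is 0.158 SD, and for 250 v 250 it is 0.175 SD. The first is a best case, as it assumes outcome data on everyone.

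**The case against.** A reader might infer that the protocol defines the primary data set by usage in place of randomisation and removes non-users from one arm. The text does not support that. Section 3.9 says all randomised participants will be evaluated, Section 9 keeps data up to withdrawal, and Section 10.1 tests the effect of group. Section 12.3 bases the primary analysis on study-website data, which do not depend on app use. In Section 3.9 the term *evaluable* explains a recruitment target and is not given as an exclusion rule. The first sentence in Section 10.1 may be only a loose description of the three-month period, and Section 3.5 describes persistence for the first cohort, whose invitation to SYD comes at baseline. A full analysis-set definition can also properly sit in an analysis plan that is not shown. All of this stands.

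It is also tempting to say that controls' Months 4-6 would enter the primary comparison. The schedule makes that untenable, since it has no assessments at Months 4 or 5.

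Nor do two one-arm details show bias. Determining drop-out in the intervention group does not rule out determining it in controls. With 1:1 randomisation, the last participants in each arm should normally reach Month 3 at about the same time.

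What the objection does not remove is the wording itself. Even read charitably, the primary-data sentence does not describe the control group, and the first-interaction origin conflicts with a Month 6 counted from joining. An analysis plan that followed these sentences would inherit the conflict.

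**Conclusion.** The concern holds as a contradiction that should be corrected. Section 10.1 describes the primary and longer-term analyses in terms that controls cannot meet within the study, and that intervention participants who never open the app cannot meet at all. Section 3.9 adds an undefined interaction criterion beside a statement that everyone randomised is evaluated. The documents do not show that non-users will be excluded.

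The harm is therefore conditional. If the usage wording were followed in the intervention arm, the comparison would lose the protection of randomisation, and it would favour SYD if users have the better prognosis. The size depends on two unknowns, the share dropped and the prognostic gap. For gaps of 0.2 to 0.5 SD, the nominal 5% error becomes about 6-11% with 10% dropped and about 15-64% with 37.5% dropped. The upper figures attribute the whole Section 3.9 allowance to intervention non-use, which the protocol does not say. The baseline adjustment planned in Section 10.1 could absorb part of the gap. These are scenarios, not predictions.

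**What to change.** Replace the two sentences in Section 10.1 with wording such as: *The primary analysis compares all randomised participants by allocated group, using Months 1-3 assessments counted from randomisation, irrespective of SYD use; longer-term analyses use Month 6 after randomisation.*

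In Section 3.9, define *evaluable* by availability of outcome data, in the same way for both arms, and drop the reference to sufficient interaction. Label analyses by level of SYD use as exploratory, and keep app-use metrics out of the model that gives the primary group effect.

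As minor tidying, report drop-out in both arms, and start the primary analysis only once the last participant in either arm has reached Month 3.

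The cost is protocol wording; no extra data are needed. The downside is that the estimated effect of offering SYD may be smaller than the effect seen among users alone.

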#### 3.2 Primary objectives

Determine the impact of SYD on Quality of Life of NHS Staff over 3 months, as measured through:

- 1. WHO Quality of Life-BREF (WHOQOL-BREF) survey (Global QOL)
- 2. EuroQoL EQ-5D-5L (Health-related QOL)

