#### SYD (See Yourself Differently) for NHS 12.3 Data sharing

The study is a research collaboration between Southern Health NHS Foundation Trust (Sponsor) and iamYiam, a company developing and testing the SYD application. Southern Health NHS Foundation Trust and iamYiam have entered into a collaboration agreement stating their responsibilities in connection with this study. Both parties have Data Controller responsibilities in relation to their respective datasets generated by this study. Data will not be shared with anyone outside of the Sponsor and iamYiam research project teams, unless needed to independently verify results at the request of regulators.

All study participants will be allocated a randomised study number at the time of joining the study. A record of participant study numbers linked to participants names and email addresses will be kept in a password protected document on the Sponsor's drive, with access strictly restricted to identified members of the research team. The primary endpoint analysis will be carried out by the Sponsor using data collected on the study website.

The Sponsor shall transfer pseudonymised study data via a secure transfer method to iamYiam for analysis and for the purpose of further research related to the SYD application use. The research study data sharing plan will be detailed on the Participant Information Sheet (PIS) and specific consent sought as part of the informed consent process.

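### As written, the mixed models that test the group effect also contain app-use metrics, so the group coefficient may not estimate the effect of being allocated to SYD

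*Protocol*

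**What the plan says.** The primary objective (section 3.2) is "Determine the impact of SYD on Quality of Life of NHS Staff over 3 months", on the WHOQOL-BREF and the EQ-5D-5L. Section 3.5 provides the comparison: "participants will be randomised 1:1 to one of two groups: Control Group and Intervention Group".

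Section 10.1 names one family of models for every score. WHOQOL-BREF and EQ-5D-5L stand in the same list as the rest: "EQ-5D index, HADS-A, HADS-D and PSS-4 scores will be modelled using linear mixed effects models". The next sentence reads "These models will be used to test the effect of group, time of measure and app-related metrics", and the metrics are illustrated as "such as type of recommendations done by participants and level of interaction with the SYD app". Adjustment for baseline characteristics is a separate sentence. Effect sizes and p-values are promised for every comparison between groups. No model for the group effect that leaves out the app metrics is described.

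On access to the app, section 6 says "Participants in the Control Group (Group B) will be invited to install and interact with the SYD smartphone mHealth app at Month 4", while the Intervention Group is invited at baseline. The schedule table agrees: the row "SYD intervention – Control Group" is marked only from Month 4 to Month 6.

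On data sources, section 12.3 says "The primary endpoint analysis will be carried out by the Sponsor using data collected on the study website". The study website holds the questionnaires. App data are gathered in the SYD platform, for which section 12.1 makes the funder the Data Controller.

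**The concern.** Randomisation protects the comparison of everyone allocated to SYD with everyone allocated to control. App use is not randomised. Participants choose it after allocation, it is the route by which an app can work, and before Month 4 no control can have any. Once use stands beside group in a model, the group coefficient answers another question: how an Intervention Group member with no use compares with a control. That is not the primary objective.

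Treating the metrics as missing in controls, rather than zero, does not help. A complete-case fit would drop every control, and imputation would invent use that could not have occurred.

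At stake is the main p-value and effect size. A real benefit could be moved from the group term to the use term, or a group difference could appear where there is none.

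**Working it through.** **Inputs from the protocol.** Two arms, 1:1; 250 evaluable per arm (section 3.9); no app access for controls before Month 4. On this point there is no stated figure to reproduce: section 3.9 gives no effect size, SD, significance level or power.

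**Assumptions.** Outcome SD 1; total effect 0.30 SD or zero; two-sided 5% test. App use U is 0 in controls and, in the Intervention Group, has mean m = 1 and coefficient of variation (CV) 0.5 or 1.0. Correlation r between use and prognosis is -0.2, 0 or +0.2. None of these is in the protocol, so ranges are shown.

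**Algebra.** Fit y = a + b·group + c·U. U does not vary in controls, so c is estimated within the Intervention Group only, and b = (difference in arm means) - c·m.

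- Effect D wholly through use, r = 0: c = D/m, so b = D - D = 0.
- No effect, use correlated r with prognosis: c = r/SD(U) = r/(CV·m), so b = -r/CV. For r = 0.2 this is -0.2/0.5 = -0.40 or -0.2/1.0 = -0.20. For r = -0.2 the signs reverse.
- Variance of b relative to the model without U: 1 + 1/(2·CV²). For CV 0.5 this is 1 + 1/0.5 = 3.0; for CV 1.0 it is 1 + 1/2 = 1.5.

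**Simulation.** 250 per arm, gamma-distributed use, least squares, 1,500 replicates per row. Each cell gives the mean group coefficient (share of replicates rejected).

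| Setting | CV | Without use | With use |
|---|---|---|---|
| Effect 0.30 wholly through use, r = 0 | 0.5 | 0.301 (0.925) | 0.006 (0.049) |
| | 1.0 | 0.299 (0.915) | -0.002 (0.049) |
| Effect 0.30 wholly through use, r = +0.2 | 0.5 | 0.302 (0.917) | -0.386 (0.703) |
| | 1.0 | 0.299 (0.889) | -0.182 (0.385) |
| Effect 0.30 not through use, r = -0.2 | 0.5 | 0.298 (0.909) | 0.682 (0.988) |
| | 1.0 | 0.299 (0.927) | 0.480 (0.995) |
| Effect 0.30 not through use, r = 0 | 0.5 | 0.302 (0.913) | 0.302 (0.504) |
| | 1.0 | 0.301 (0.912) | 0.301 (0.785) |
| No effect, r = +0.2 | 0.5 | 0.006 (0.049) | -0.382 (0.697) |
| | 1.0 | 0.004 (0.067) | -0.180 (0.378) |
| No effect, r = -0.2 | 0.5 | 0.001 (0.047) | 0.392 (0.724) |
| | 1.0 | 0.002 (0.059) | 0.183 (0.389) |

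The null rows lie close to -r/CV. They fall slightly short because the correlation was set on an underlying normal score rather than on use itself. Variance ratios under no effect were 2.97 to 3.03 (CV 0.5) and 1.49 to 1.51 (CV 1.0), as the formula predicts.

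**Mixed-model check.** Random intercept, Months 1-3, CV 1.0, only 20 replicates per setting. Adding use moves the group coefficient from 0.32 to 0.02 (effect through use, r = 0), from 0.30 to -0.18 (effect through use, r = +0.2) and from -0.02 to -0.21 (no effect, r = +0.2). The pattern is the same.

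**The case against.** The strongest reply is that section 10.1 writes no equation. Its sentence can be read as a list of effects tested across several models. Only baseline characteristics are named as adjusters, and one of the example metrics has no meaning for a control before Month 4, so a separate model within the Intervention Group is conceivable. Section 12.3 supports this reply. If the primary analysis rests on study-website data, it has no app metrics in it, and the only transfer of data described there runs from the Sponsor to the funder. This stands in part: joint entry is the natural reading, not an explicit statement. But section 10.1 attaches the metrics to the same models that cover the primary instruments and offers no alternative, so section 12.3 conflicts with it without settling the matter. Section 10.1 also says that analyses will be descriptive only, which does not fit with models and p-values either.

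A second reply is that this is a pilot, described in section 3.9 as not a superiority trial and sized for confidence intervals. That lowers the stakes. It does not remove them, because section 10.1 still states a null hypothesis and promises p-values, and a confidence interval around the wrong contrast is no better than a test of it.

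A reader might also infer that the group effect is diluted by averaging over Month 0, when no effect is possible, and Month 6, when controls have SYD. The documents do not support the Month 6 part: sections 8 and 10.1 place the primary analysis at 3 months and treat longer-term effects separately. Whether Month 0 is an outcome or a covariate, and whether a group-by-time term is fitted, are details commonly left to a statistical analysis plan; their absence here is not a fault.

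**Conclusion.** The concern holds on the natural reading of section 10.1. If group and app use share a model, the group coefficient through Month 3 is a contrast at zero use and does not answer the primary objective. Under the assumptions shown, a 0.30 SD effect acting wholly through use falls to about 0. With no effect and r = ±0.2, the bias is about 0.2 SD (CV 1.0) to 0.4 SD (CV 0.5) in either direction, with false rejection of 38% to 72%. If use neither mediates nor predicts outcome, there is no bias, but the variance rises 1.5- to 3-fold and power falls from about 0.91 to 0.79 or 0.50.

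A reader might infer that the model must hide a benefit or show harm. The documents do not support that: they give no usage distribution and no link between use and outcome, and the coefficient can equally be inflated. Nor can it be said that the protocol firmly commits to the joint model, given section 12.3. The fault of zero use in every control is confined to Months 0-3; by Month 6 controls have had the app, and use is still post-randomisation but no longer zero by design. The point should be corrected before analysis, but it does not undermine the design.

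**What to change.** In section 10.1, state that the primary group comparison over Months 1-3 includes all randomised participants, with group, month, group-by-month and the Month 0 score (plus any prespecified baseline covariates), and without app metrics. Describe the app metrics in a separate sentence as an exploratory analysis within the Intervention Group, where an association with outcome is not read as the effect of SYD. Reconcile section 10.1 with section 12.3 by saying which analyses use study-website data alone and which need app data. The cost is a change of wording and one additional exploratory model. No new data are needed.
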